## 9. SAFETY AND REPORTABLE EVENTS

For study purposes, adverse events will be categorized at the investigative site into 2 groups: Relatable (Expected) Adverse Events (Grade 1-3) or Serious Adverse Events (Grade 4-5). Therefore, any AEs that are not relatable to the devices, themselves, will not be collected for study purposes. However, all non-relatable AEs will be recorded on the anesthesia record. The PI will determine if the event is related to the device or its deployment, or not related to the device or its deployment will assess the causal relationship of each adverse event.

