### 9.1 Adverse Events Definitions

An adverse event (AE) is any undesirable clinical event occurring to the subject during a clinical study, whether or not it is considered related to the investigational product. This includes a change in a subject's condition or laboratory results, which has or could have a deleterious effect on the subject's health or well-being. An Adverse Event that is related to the investigational device may be referred to as an Adverse Device Effect (ADE). If any of the above-mentioned events occurs, the study will be terminated and case will report according to the standard clinical pathway.

An adverse event does not include:

- Medical or surgical procedures; the condition that leads to the procedure is not an adverse event
- Pre-existing disease, conditions, or laboratory abnormalities present at the start of the study that do not worsen in frequency or intensity
- Situations where an untoward medical occurrence has not occurred (e.g., hospitalizations for cosmetic or elective surgery or social/convenience admissions)
- Expected post-operative course

**Unanticipated Adverse Device Effect (UADE):** Any device related adverse event, the nature or severity of which is not consistent with or listed in the applicable product information (e.g., instructions for use, subject informed consent document, subject information brochure [if applicable], promotional literature) or any other unanticipated serious problem associated with a device that relates to the rights, safety, or welfare of subjects.

A serious adverse event (SAE) is defined as any adverse medical experience that results in any of the following outcomes:

- Death;
- Is life threatening;
- Requires inpatient hospitalization or prolongation of existing hospitalization;
- Results in persistent or significant disability/incapacity;

- Requires medical/surgical intervention to prevent permanent impairment or damage

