## 9.2 Reporting of Adverse Events

All adverse events, whether observed by the PI or study coordinator, elicited from or volunteered by the subject, should be documented. Each adverse event will include a brief description of the experience, the date of occurrence, the date of resolution, the duration and type of experience, the severity, the relationship to investigational product (i.e., drug or device), contributing factors, and any action taken with respect to the study drug/device.

Investigators and research coordinators will be instructed that all AE and corresponding relevant information should be recorded on the Adverse Event Form. In addition, the clinical site will be responsible for notifying the Sponsor within 24 hours of any UADE. All relevant information regarding an UADE should be recorded on the Adverse Event Form and reported to Sponsor via Fax within 24 hours of the event. In addition to the event form, copies of adverse device effect related source documents should be forwarded to the Sponsor.

The Principal Investigator is responsible for reporting AEs to the IRB of record in accordance with IRB procedures. The Sponsor is responsible for informing the appropriate regulatory authorities and other Investigators of any UADEs that have occurred.

The device used in the study is standard anesthesia equipment; further, the study is no more than a data collection process via routine anesthesia care, no modification from routine practice added to a study subject. Therefore, other than general precaution and potential risks from corresponding anesthesia care, the study itself does not have added risk to a study subject other than data collection. No additional risk justification needed for the study.

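### Section 9 labels all device-related Grade 1-3 events as expected, which conflicts with the grade-free UADE definition in Section 9.1 and risks a missed or late UADE report

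*Combined protocol and SAP*

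**What the plan says.** Section 9 (Safety and Reportable Events) has adverse events "categorized at the investigative site into 2 groups: Relatable (Expected) Adverse Events (Grade 1-3) or Serious Adverse Events (Grade 4-5"). It adds that events unrelated to the devices are not collected for study purposes and go only on the anesthesia record. The PI decides relatedness. Section 9 assigns nobody the decision on expectedness.

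Section 9.1 (Adverse Events Definitions) gives two definitions that do not use grade. The first part of the UADE definition reads "Any device related adverse event, the nature or severity of which is not consistent with or listed in the applicable product information". The SAE definition begins "A serious adverse event (SAE) is defined as any adverse medical experience that results in any of the following outcomes" and then lists outcomes such as death, threat to life and hospitalization.

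Section 9.2 (Reporting of Adverse Events) lists what is recorded: "Each adverse event will include a brief description of the experience, the date of occurrence, the date of resolution, the duration and type of experience", then "the severity, the relationship to investigational product (i.e., drug or device), contributing factors, and any action taken with respect to the study drug/device". It also says that "the clinical site will be responsible for notifying the Sponsor within 24 hours of any UADE", and it sends UADE information to the Adverse Event Form.

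**The concern.** Relatedness, expectedness and seriousness are three different judgements. Relatedness asks whether the device caused the event. Expectedness asks whether the event matches what is already documented for the device. Seriousness asks about outcome. Section 9 merges the first two for Grades 1 to 3 and ties the third to Grades 4 and 5.

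This matters because several duties depend on someone at the site recognizing a UADE: the 24-hour notice and the Sponsor's duty to inform authorities (Section 9.2), and the Sponsor's prompt notification and its report of an evaluation within 10 working days (Section 9.7). The only sorting rule given to the site points away from that recognition for low and middle grades. The Background says that how the device performs in patients at high risk of obstruction under TIVA is not yet clear, so there is little basis for presuming that whatever it causes at Grade 1 to 3 is already known.

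**Working it through.** There is no arithmetic to reproduce. The point rests on setting the sections side by side.

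| Question | Section 9 | Section 9.1 | Section 9.2 item list |
|---|---|---|---|
| Is the event related to the device? | PI decides; unrelated events are not collected for the study | Required by the first part of the UADE definition | Listed |
| Is the event expected? | Yes, if related and Grade 1-3 | Decided against the product information, at any grade | Not listed |
| Is the event serious? | Yes, if Grade 4-5 | Decided by outcome | Not listed (severity is) |

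**Step 1: a related, unlisted Grade 2 event.** Under Section 9 it cannot go in the Grade 4-5 group, so it goes in the only other one, which is labelled expected. Under Section 9.1 it is device-related and its nature is not in the product information, so it is a UADE. The two sections give opposite answers for the same event.

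**Step 2: how much of the scale is affected.** The label covers Grades 1, 2 and 3, which is three of five grades. Neither of the two groups is provided for an unexpected device effect. Because unrelated events are left out of study collection, the Grade 1-3 group is exactly where any UADE of those grades would be placed.

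**Step 3: does the record prompt a correction?** The items listed in Section 9.2 are description, dates of occurrence and resolution, duration, type, severity, relationship, contributing factors and action taken. Expectedness is not among them. The listed items supply raw material for the comparison with the product information, but none asks for the result.

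**Step 4: seriousness.** A Grade 3 device-related event that leads to hospitalization is an SAE by the Section 9.1 outcomes, but Section 9 puts it in the expected group. Severity grade and seriousness by outcome are different attributes, and the Section 9.2 list has only the former.

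**Step 5: does the reporting duty depend on the Section 9 group?** No. Section 9.2 requires "notifying the Sponsor within 24 hours of any UADE", and the term is defined in Section 9.1 without reference to the groups. The duty survives the misclassification. What the misclassification threatens is recognition of the event, and so whether the report is made and made on time.

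**The case against.** The strongest reply is that the label is loose drafting and the reporting chain is intact. Four parts of it deserve weight.

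- **The duty is not switched off.** A reader might infer that the 24-hour report is never triggered for Grade 1-3 events. The text does not say so: the duty applies to every UADE and the definition has no grade limit. This part of the reply stands in full.
- **The form has not been seen.** A reader might infer that the Adverse Event Form lacks expectedness and seriousness fields. Appendix A is listed by title only, and Section 9.2 says UADE information goes on that form, so it may have a suitable field. Only the list in Section 9.2 can be checked. Section 9.3 also has the PI record serious events in source documents or the AE log.
- **There are second checks.** Section 11.3 has the Sponsor review all CRFs, review adverse events and evaluate UADEs promptly. Section 9.2 has the PI report adverse events to the IRB, and Section 10.2 says an identifiable event is handled and reported. These lower the risk. They are weaker protection for a 24-hour deadline, because Section 11.3 makes interim monitoring as needed and requests further documents once a UADE has been observed and reported.
- **The control arm is not clearly excluded.** A reader might infer from the wording on investigational product that an event caused by the non-rebreather mask cannot be recorded. Section 9 speaks of devices in the plural, and the Section 9.2 list includes contributing factors, so this is not established.

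What the reply does not remove is the contradiction itself. A form with a UADE box would still sit beside a Section 9 rule that calls the same event expected.

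**Conclusion.** The concern holds as an internal contradiction with a practical risk. Section 9 treats expectedness as following from grade and relatedness, Section 9.1 treats it as a comparison with product information, and the Section 9.2 list does not ask for it. A site that follows the Section 9 categories could file a Grade 1-3 UADE as expected and miss or delay its report.

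Its size is three of five grades and every device-related event within them. It cannot be put as a number of missed reports: the documents give no rate of device effects, and an assumed rate would give only the chance that an event occurs, not that its report fails. Nor should it be inferred that a final safety table will show all such events as expected, since Section 6.2 plans no such table. The primary endpoint and its analysis are unaffected.

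The conclusion assumes that the label in Section 9 is meant to be applied as written. If the site ignores it and works from Section 9.1 alone, the risk falls, but the text still needs reconciling.

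**What to change.** Reconcile Section 9 with Section 9.1:

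1. In Section 9, remove the word expected as a property of grade and relatedness.
2. Record three separate attributes for each collected event: relatedness, expectedness against the applicable product information, and seriousness by the Section 9.1 outcomes. Keep severity grade as its own item.
3. Add expectedness and seriousness to the Section 9.2 list, and to the Adverse Event Form if they are not already there.
4. State that a device-related event that departs from the product information is handled as a UADE under Section 9.2 at any grade.

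The cost is a wording amendment and at most two form items. It needs no extra patients, visits or procedures.

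### Section 9 keeps adverse events unrelated to the devices out of the study data, Section 9.2 puts every adverse event on the Adverse Event Form, and nothing says which rule prevails

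*Combined protocol and SAP*

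**What the plan says.** All of the relevant text is in the safety part of the combined protocol and SAP.

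- **Section 9 (Safety and Reportable Events), collection.** It says that "any AEs that are not relatable to the devices, themselves, will not be collected for study purposes", and adds that "all non-relatable AEs will be recorded on the anesthesia record". Attribution rests with one person: "The PI will determine if the event is related to the device or its deployment".
- **Section 9, grouping.** AEs are sorted at the site into two groups: "Relatable (Expected) Adverse Events (Grade 1-3) or Serious Adverse Events (Grade 4-5").
- **Section 9.1 (Adverse Events Definitions).** An AE is defined regardless of its relationship to the product. Seriousness is defined by outcome: "A serious adverse event (SAE) is defined as any adverse medical experience that results in any of the following outcomes". Five outcomes follow, among them "Requires inpatient hospitalization or prolongation of existing hospitalization". None is expressed as a grade.
- **Section 9.2 (Reporting of Adverse Events).** "Investigators and research coordinators will be instructed that all AE and corresponding relevant information should be recorded on the Adverse Event Form". The items to be recorded for each event include "the date of resolution, the duration and type of experience, the severity, the relationship to investigational product". The PI also reports AEs to the IRB under the IRB's own procedures.
- **Section 9.3 (Responsibilities for Reporting Serious Adverse Events).** The PI records all serious events of the study period in source documents, an AE log, or both. No condition on relatedness is attached.

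**The concern.** Two adjacent sections give opposite instructions for the same event. A coordinator who follows Section 9 leaves an unrelated AE off the study forms. One who follows Section 9.2 enters it and marks it unrelated. Both can point to the protocol.

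The choice matters because of who makes the attribution and how. Under Section 9 the PI's judgement becomes the condition for entry, and the protocol describes no blinding of that judgement in a trial that compares a high-flow nasal device with a mask. Filtering on attribution before data entry also means that the study data cannot later show how the attribution was made or how many events it removed.

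A second, conditional problem concerns seriousness. Section 9 attaches the serious label to a grade range without naming a scale in the text, and Section 9.1 attaches it to outcomes. If the scale in use allows a lower-graded event to meet one of those outcomes, the count of serious events depends on which section staff apply.

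**Working it through.** No arithmetic applies: the plan states no AE rate, no attribution share and no grading scale. The check sets the rules side by side and follows single events through them.

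**Collection**

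| Event | Section 9 | Section 9.2 | Section 9.3 |
|---|---|---|---|
| Non-serious, judged related | collected | on the Adverse Event Form | not addressed |
| Non-serious, judged unrelated | not collected; anesthesia record | on the Adverse Event Form, relationship recorded | not addressed |
| Serious by 9.1, judged unrelated | not collected, if the filter is read as covering serious events | on the Adverse Event Form, relationship recorded | recorded by the PI, but source documents alone suffice |

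1. The first row raises no conflict.
2. In the second row, one event counts 1 on the form under 9.2 and 0 in the study data under Section 9.
3. Under 9.2, 100% of AEs reach the form. Under Section 9, the share of non-serious AEs collected equals the share that the PI calls related. The documents do not give that share, so it could lie anywhere from 0% to 100%.
4. In the third row, 9.3 ensures that the event is recorded somewhere, but not on a study form.
5. Could the anesthesia record satisfy 9.2? It could satisfy that section's general requirement to document AEs. It does not satisfy the next instruction, which names the Adverse Event Form for all of them. Moreover, if only related events were collected, recording relationship for each one could not separate related from unrelated.
6. Sections 9 to 9.3 and the rest of the protocol contain no statement of precedence.

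**Seriousness**

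1. Section 9 uses one cut-off: Grades 4-5 are serious, Grades 1-3 are not.
2. Section 9.1 lists five outcomes, of which 0 are expressed as a grade.
3. No scale is named in the text and no grade is mapped to an outcome. Appendix A lists the case report forms but does not reproduce them.
4. Suppose the scale allows a Grade 3 event to prolong hospitalization. That event is serious under 9.1 (count 1) and not under Section 9 (count 0). If the scale allows no Grade 1-3 event to meet any 9.1 outcome, this divergence does not arise. The text does not show which case applies.

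**The case against.** The strongest reply is that little depends on this. The relatedness filter has no effect on the primary endpoint, total length of desaturation episodes (ToLDE). Neither the objectives nor Section 6 plans an AE comparison. Section 7 collects desaturation and airway-support episodes for all patients, whatever the attribution. AEs also go to the IRB, and Section 11.3 provides for comparison of case report forms with source documents. All of this stands and keeps the point minor. Monitoring does not remove it, however: an unrelated AE on the anesthesia record but absent from the form is an omission under 9.2 and correct under Section 9, so the monitor has no stated rule to apply.

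A second reply is that only 9.1 claims to define a serious event, and that the grades in Section 9 are a sorting label. That is a fair reading, and it is why the seriousness point is conditional. A reader might infer that serious-event counts are bound to differ between the sections; without a named scale, the documents do not show that.

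A third reply is that Section 9 lists serious events apart from the relatable group, so the filter may not reach them, and 9.3 records all of them in any case. This narrows the gap for serious events. It does not close it, because 9.3 can be met without any study form.

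A reader might also infer that biased AE figures will be passed to later studies. The planning purpose stated in Section 1 concerns device performance, and no AE figure is planned for that use, so this harm is conjectural.

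Finally, narrowing 9.2 would also remove the contradiction. That is true, but it would leave attribution, with no blinding described, as the condition for entry.

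**Conclusion.** The contradiction on collection holds on the current text and needs no assumption about rates: an AE judged unrelated is in the study record under 9.2 and out of it under Section 9, with no rule to choose between them. The seriousness conflict holds only under a grading scale that lets a Grade 1-3 event meet a 9.1 outcome.

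Severity is minor. The size is one event in or out for each AE judged unrelated, and no total can be derived. The effect of the filter on the ToLDE estimate is 0. The text does not support a claim that safety results will be biased between arms, or that serious events will go unrecorded.

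The conclusion rests on the protocol text alone. It assumes that the Appendix A forms, which are not reproduced, carry no instruction that settles the matter.

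**What to change.** 1. Delete the Section 9 sentence that keeps unrelated AEs out of the study data, so that 9.2 governs in both arms. Relatedness is then a field on the Adverse Event Form and not a condition for entry.
2. State that seriousness follows the 9.1 outcomes. Record grade separately, as severity, on a scale named in the protocol.

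The cost is protocol wording and a small amount of extra data entry for events that would otherwise stay only on the anesthesia record. No AE test or added analysis is needed.

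A separate matter for its own correction: Section 9.1 speaks of terminating the study, and Section 10.2 of terminating data collection, when an adverse event occurs. Those statements should be reconciled with each other and with 9.2, which asks for the duration and resolution of each event.

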### 9.1 Adverse Events Definitions

An adverse event (AE) is any undesirable clinical event occurring to the subject during a clinical study, whether or not it is considered related to the investigational product. This includes a change in a subject's condition or laboratory results, which has or could have a deleterious effect on the subject's health or well-being. An Adverse Event that is related to the investigational device may be referred to as an Adverse Device Effect (ADE). If any of the above-mentioned events occurs, the study will be terminated and case will report according to the standard clinical pathway.

An adverse event does not include:

- Medical or surgical procedures; the condition that leads to the procedure is not an adverse event
- Pre-existing disease, conditions, or laboratory abnormalities present at the start of the study that do not worsen in frequency or intensity
- Situations where an untoward medical occurrence has not occurred (e.g., hospitalizations for cosmetic or elective surgery or social/convenience admissions)
- Expected post-operative course

**Unanticipated Adverse Device Effect (UADE):** Any device related adverse event, the nature or severity of which is not consistent with or listed in the applicable product information (e.g., instructions for use, subject informed consent document, subject information brochure [if applicable], promotional literature) or any other unanticipated serious problem associated with a device that relates to the rights, safety, or welfare of subjects.

A serious adverse event (SAE) is defined as any adverse medical experience that results in any of the following outcomes:

- Death;
- Is life threatening;
- Requires inpatient hospitalization or prolongation of existing hospitalization;
- Results in persistent or significant disability/incapacity;

- Requires medical/surgical intervention to prevent permanent impairment or damage

## 9.2 Reporting of Adverse Events

All adverse events, whether observed by the PI or study coordinator, elicited from or volunteered by the subject, should be documented. Each adverse event will include a brief description of the experience, the date of occurrence, the date of resolution, the duration and type of experience, the severity, the relationship to investigational product (i.e., drug or device), contributing factors, and any action taken with respect to the study drug/device.

Investigators and research coordinators will be instructed that all AE and corresponding relevant information should be recorded on the Adverse Event Form. In addition, the clinical site will be responsible for notifying the Sponsor within 24 hours of any UADE. All relevant information regarding an UADE should be recorded on the Adverse Event Form and reported to Sponsor via Fax within 24 hours of the event. In addition to the event form, copies of adverse device effect related source documents should be forwarded to the Sponsor.

The Principal Investigator is responsible for reporting AEs to the IRB of record in accordance with IRB procedures. The Sponsor is responsible for informing the appropriate regulatory authorities and other Investigators of any UADEs that have occurred.

The device used in the study is standard anesthesia equipment; further, the study is no more than a data collection process via routine anesthesia care, no modification from routine practice added to a study subject. Therefore, other than general precaution and potential risks from corresponding anesthesia care, the study itself does not have added risk to a study subject other than data collection. No additional risk justification needed for the study.

